8.3 Safety objective

Safety objective	Corresponding primary endpoint/outcome variable(s)	Section
L. To investigate the occurrence and severity of adverse events related to the investigational device and associated procedures	1. Number and severity of related adverse events reported from surgery throughout the investigation at 3- and 12 months	10.4
	2. Number and severity of device deficiencies reported from surgery throughout the investigation at 3- and 12 months	10.4

CONFIDENTIAL

8.4 Risks and anticipated adverse device effects that are to be assessed

Anticipated device effects are summarized in section 7.1. In the investigation the principal investigator or designee is responsible for judging whether the appearance of any adverse event, including the events mentioned in section 7.1, are considered to be AEs or ADEs. Applicable events must be reported in the applicable section of the eCRF (according to the timelines and definitions mentioned in the AE section (section 19.3)).

9 DESIGN OF THE CLINICAL INVESTIGATION

9.1 Investigation outline

This investigation is a 12-months prospective, multinational, multicentre, single-arm investigation on the performance and safety of the Ponto implant system implanted using the MONO surgical procedure. The primary aim of the study is to investigate the proportion of patients that are able to use their sound processor as intended three months after implantation, taking into consideration several different variables such as implant stability, skin reactions and pain. This composite endpoint is anticipated to be the most relevant outcome for the patient as it focuses on the usability of the device, which is the decisive factor for patient benefit. Additional outcomes investigated in the study include implant stability and survival, surgery length, subjective pain and numbness, skin conditions around the abutment, sound processor usage and patient benefit in terms of quality of life-questionnaire. In addition to primary endpoint data, long-term safety and performance will be evaluated over a 12-months period (Figure 4).

[figure not shown]

Figure 4. Overview of the clinical investigation

Patients considered for inclusion into this clinical investigation will be found among those who have already received audiological and otological evaluation and are found to be suitable candidates for BAHS treatment. Potential subjects will be asked by their ENT specialist to participate in the investigation, with the aim to include a total number of 50 subjects across all investigation sites. An informed consent form must be signed by the subject and investigator (or delegated site staff) before any procedures related to the investigation are performed and also before any information is recorded in the study-specific eCRFs.

Following screening and surgery, subjects will come for post-operative follow-up visits at 9 days*, 5 weeks*, 3 months, 6 months, and 12 months following implant installation. With some minor deviations, it is routine clinical practice for patients to visit the clinic at these intervals for follow-up. At each visit, a clinical evaluation of the surgical site and implant will be made, and a range of outcome measures related to implant, skin status and post-operative events are collected. Sound processor fitting/implant loading will be scheduled according to local clinical practice, which may vary across study sites and may fall outside the data collection visit intervals defined in this protocol. If the loading visit constitutes an additional follow-up not accounted for in the schedule, the study participant will be screened for adverse events and referred immediately for physical examination if necessary. At all visits, study participants will be screened for adverse events and referred immediately for physical examination if necessary.

*Will vary between the study sites, depending on their normal follow-up schedules.

All clinical and investigation-related data will be recorded in eCRFs. A schematic overview of the investigation visits and collected variables is shown in Table 4.

9.1.1 Clinical Investigation flow chart

Table 4. Flow chart of the investigation

Protocol activity	V1	V2	V3	V4	V5	V6	V7	Un-scheduled visit(s)
	Screening	Surgery	Surgical follow-up	Follow-up	Follow-up (Primary endpoint)	Follow-up	Follow-up (End of study)	
	Pre-surgery	0	9 days	5 weeks**	3 months	6 months	12 months	
			± 3 days	± 2 weeks	± 1 week	± 2 weeks	± 1 month	
Subject Eligibility								
Informed consent	X							
Inclusion/exclusion criteria	X	X						
Baseline characteristics	X							
Medical and surgical history	X							
Audiology								
Fitting Sound Processor*				X	X			
Implantation								
Surgical information		X						
Intra-operative events		X						
Post-operative assessment								
Post-operative events			X	X	X	X	X	X
Skin assessments			X	X	X	X	X	X
Implant survival			X	X	X	X	X	X
Manual implant stability			X	X	X	X	X	X
Subjective pain and numbness assessment	X		X	X	X	X	X	X
Sound processor usage				(X)	X	X	X	
PRO's								
GBI					X			
Safety								
Adverse events assessment		X	X	X	X	X	X	(X)

* Sound processor fitting will occur according to local clinical practice, but no later than at the 3-month follow-up visit.

** The extended visit window is due to different local clinical practices regarding post-operative follow-up.

9.2 Clinical investigation visits

When a subject has agreed to participate in the clinical investigation, the following assessments, measurements and/or actions will be performed, and corresponding data will be collected and recorded in the eCRF.

9.2.1 Visit 1: Screening

- Informed consent is obtained from the subject (see section 18)
- The subject is evaluated in respect to inclusion and exclusion criteria
- The subject's demographic data is collected and recorded

CONFIDENTIAL

oticon MEDICAL	Title BC108 CIP MONO	Document no Doc-00068506	Revision 2	Page 25(48)
--------------------------	--------------------------------	------------------------------------	----------------------	-----------------------

- Data concerning the patient's hearing impairment; medical history, and ongoing diseases and treatments, is recorded
- Pre-operative pain and numbness in the area of implant installation is assessed

9.2.2 *Visit 2: Surgery (and implant installation)*

- Surgical information recorded (see section 10.2)
- Medications given perioperatively recorded
- Intra-operative events (see section 10.2.3)

9.2.3 *Visit 3: Surgical follow-up*

- Removal of dressings and healing cap
- Implant survival (see section 10.3.2)
- Implant stability (see section 10.3.3)
- Skin condition assessments (see section 10.3.4)
- Pain assessment (see section 10.3.6)
- Numbness assessment (see section 10.3.7)
- Assessment of post-operative events (see section 10.3.5)
- Safety assessment with collection of adverse events (see section 10.4)
- The patient is instructed on cleaning procedures

9.2.4 *Visit 4–7: Follow-ups*

- Implant survival
- Implant stability
- Skin condition assessments
- Pain assessment
- Numbness assessment
- Assessment of post-operative events
- Safety assessment with collection of adverse events
- Type of sound processor is recorded
- Average sound processor usage time is recorded (see section 10.3.8)
- Completion of GBI questionnaire (see section 10.3.9.1**Error! Reference source not found.**) (visit 5)

9.3 Investigational device

The investigational device is the MONO Surgery kit that is to be used in BAHS surgeries during temporal bone drilling, allowing for insertion of a Ponto implant. Further details on the investigational device can be found in section 5.1**Error! Reference source not found.**

A new MONO Surgery kit is to be used for every surgery (single use), resulting in a total of at least 50 kits to be used in the study. (Extra kits will be provided to investigators to allow for bilateral surgeries.)

Other medical devices to be used in the investigation are listed in Table 5.

Table 5. Overview of devices to be used in the investigation and corresponding article numbers

Name	Article number	Description
Ponto BHX implant, 4 mm, with abutment, 6 mm	52168	The 4 mm Ponto BHX implant with pre-mounted 6 mm abutment is used in the single-stage surgical procedure and consists of implant, abutment and connection screw.
Ponto BHX implant, 4 mm, with abutment, 9 mm	52169	The 4 mm Ponto BHX implant with pre-mounted 9 mm abutment is used in the single-stage surgical procedure and consists of implant, abutment and connection screw.
Ponto BHX implant, 4 mm, with abutment, 12 mm	52170	The 4 mm Ponto BHX implant with pre-mounted 12 mm abutment is used in the single-stage surgical procedure and consists of implant, abutment and connection screw.
Ponto BHX implant, 4 mm, with abutment, 14 mm	52171	The 4 mm Ponto BHX implant with pre-mounted 14 mm abutment is used in the single-stage surgical procedure and consists of implant, abutment and connection screw.
Ponto wide implant, 4 mm, with abutment, 6 mm	51136	The 4 mm implant is used in the single-stage surgical procedure and consists of a pre-mounted 6 mm abutment, a connection screw and a 4 mm wide implant.
Ponto wide implant, 4 mm, with abutment, 9 mm	51137	The 4 mm implant is used in the single-stage surgical procedure and consists of a pre-mounted 9 mm abutment, a connection screw and a 4 mm wide implant.
Ponto wide implant, 4 mm, with abutment, 12 mm	51138	The 4 mm implant is used in the single-stage surgical procedure and consists of a pre-mounted 12 mm abutment, a connection screw and a 4 mm wide implant.
Ponto wide implant, 4 mm, with abutment, 14 mm	52065	The 4 mm implant is used in the single-stage surgical procedure and consists of a pre-mounted 14 mm abutment, a connection screw and a 4 mm wide implant.
Sound processor indicator	50428	The sound processor indicator is used on intact skin to illustrate the size of a sound processor in order to assess and enable marking of the appropriate implant site prior to incision.
Sterilisation cassette	52074	Sterilisation cassette holds instruments in place during sterilisation.
Counter torque wrench	51690	The counter torque wrench is used for counteracting the force when tightening or unscrewing the connection screw using the screwdriver. It is also used for manual tightening in the single-stage procedure if needed.
Torque wrench	50230	The Torque wrench, scale 10–35 Ncm, is used to secure the correct torque when tightening the connection screw. It is used together with the screwdriver handle.
Ruler	52143	The ruler is used to measure the thickness of the patient's skin before surgery and to guide the selection of the appropriate abutment length.
Double-ended dissector	52196	The Double-ended dissector is used for dissection and removal of the periosteum. The blunt side is also used for inspection of bone.
Handle with screwdriver	50437	The screwdriver handle with replaceable bits can be used together with the torque wrench. It is delivered with one screwdriver machine bit.
Insertion indicator	52366	Insertion indicator is used as a guide to visualise installation of the implant.
Abutment inserter, machine	51695	The abutment inserter is used during the single-stage surgical procedure for inserting the implant with the pre-mounted abutment, using the drill equipment. The shaft has a hexagonal collar with a shaft fitted according to ISO 1797-1.
Square fit connection	50386	The square fit connection is used for inserting the 3 and 4 mm implant with the pre-mounted implant adapter, using the drill equipment. The shaft is fitted according to ISO 1797-1.
Screwdriver, machine, 35mm	50384	The screwdriver machine bit can be used with both the screwdriver handle and the drill equipment handpiece. The bit fits all the abutment connection screws and the implant adapter screws. The shaft is fitted according to ISO 1797-1.

No comparator device will be used in the investigation.

9.4 Subject population

Patients considered for inclusion into this clinical investigation will be found among those who have already received audiological and otological evaluation and are found to be suitable candidates for BAHS treatment.

9.4.1 *Inclusion criteria*

1. 18 years of age or older
2. Patient indicated for surgical intervention with a bone anchored hearing system
3. Signed informed consent
4. Adequate bone quality to allow for a Ponto implant insertion, as judged by the investigator, and an expected bone thickness above 5 mm, where no complications during surgery are expected
5. Skin thickness of 12 mm or less at the implant site

9.4.2 *Exclusion criteria*

Subjects meeting any of the following criteria will not be permitted to participate in the investigation:

1. Patient undergoing re-implantation
2. Patient who are unable or unwilling to follow investigational procedures/requirements, e.g. to complete quality of life scales
3. Known condition or previous treatment that could jeopardize skin condition and wound healing over time as judged by the investigator (e.g. uncontrolled diabetes, previous radiotherapy in the area of interest)
4. Known medical condition that contraindicate surgery as judged by the investigator
5. Known and/or planned pregnancy at time of surgery
6. Any other known condition that the investigator determines could interfere with compliance or investigation assessments
7. Simultaneous participation in another clinical investigation with pharmaceutical and/or medical device which might cause interference with investigation participation

9.4.2.1 *Relationship of investigation population to target population*

The investigation population correlates very well to the target population of the investigational device (see section 5.5). Adult patients with all types of indicated hearing losses, whether uni- or bilateral fitted, are potentially eligible for inclusion. Patient participation is completely voluntary. Patient groups not included in the investigation relates to diseases or conditions that may compromise skin conditions, pregnancy, cognitive impairment or any other known condition that could interfere with compliance of the investigation. These patient groups may be treated outside of the study if judged suitable by the treating physician.

9.4.3 *Number of Subjects*

A total of 50 patients will be included in the investigation. All potential subjects are already planned for treatment with a percutaneous bone-anchored hearing device and will be consecutively included in the investigation using the inclusion and exclusion criteria stated above. Bilateral surgeries are allowed. Bilaterally operated patients will account as one patient out of the 50, whereas both implant/abutment complexes will be accounted for in the implant-level analyses. The investigation will be performed at seven different sites with a maximum of 15 and an intended minimum of three subjects per site.

CONFIDENTIAL

The investigation will be performed at the following sites:

1. Guy's and St Thomas' Hospitals, London, UK
2. Addenbroke's Hospital, Cambridge, UK
3. Queen Elizabeth Hospital, Birmingham, UK
4. Sahlgrenska University Hospital, Gothenburg, Sweden
5. Aalborg University Hospital, Aalborg, Denmark
6. Odense University Hospital, Odense, Denmark
7. Radboud University Medical Center, Nijmegen, The Netherlands

Subject inclusion is estimated to start in the last quarter of 2020, depending on when approvals from concerned ethical committees are granted. The recruitment period will be ongoing until the total number of subjects has been reached and is estimated to last for approximately 6 months. The end of the investigation is therefore expected to be around the end of the second quarter in 2022, i.e. a total study duration of 1.5 year. Since the primary endpoint is due at the 3-month visit, corresponding data will be extracted, analysed and reported as applicable, with an approximate start in the end of the third quarter in 2021. The total duration of the investigation for each subject is 12 months (from implant installation date).

Expected time schedule for investigation milestones

Start of enrolment:	Q4 2020
End of enrolment:	Q2 2021
Primary endpoint:	Q3 2021
End of study:	Q2 2022

9.4.4 Criteria and procedures for subject withdrawal or lost to follow up

Subjects are free to discontinue participation in the investigation at any time without affecting the medical care of the subject. If a subject withdraws from the clinical investigation, the reason(s) shall be recorded. If such withdrawal is due to problems related to the investigational device safety or performance, the investigator shall ask for the subject's permission to follow his/her status/condition outside the clinical investigation.

Withdrawal criteria:

- Unwillingness to continue participation in the study
- Loss of implant placed during the study (extrusion or elective removal)
- Patients lost to follow-up (following three documented contact attempts)

Subjects withdrawing from the investigation after implantation will not be replaced. Collected data will be considered as far as possible in analyses.

9.4.5 Information on vulnerable, pregnant and breastfeeding population

In the investigation, recruitment will occur among patients already approved for a bone-anchored hearing system. Persons considered as vulnerable, e.g. due to cognitive disability or pregnancy, will not be considered for study inclusion. If pregnancy would be detected during the course of the study (after surgery), no harm is expected during the post-operative assessments and it is safe for the patient to continue throughout the investigation. The study includes no invasive procedure during follow-up. Also, no procedure-related medication will be given during follow-up unless needed for treatment of possible complications. Breastfeeding women are at no increased risk to participate in

the study.

10 CLINICAL INVESTIGATION PROCEDURES

The investigation-related procedures that the subjects undergo during the clinical investigation as well as the data assessed at specific visits are outlined below. All activities are performed by hospital personnel delegated by the principal investigator, e.g. surgeon, nurse or audiologist (i.e. not performed by the sponsor). After the clinical investigation is completed, all patients will be followed-up according to the clinics' routine practice.

10.1 Screening

The following subject demographic and other baseline characteristics will be collected at the screening visit:

- Gender
- Age (calculated from date of birth: DD-MM-YYYY)
- Ethnicity
- BMI (calculated from weight and height)
- Relevant medical and surgical history
 - e.g. skin diseases, diabetes, irradiation etc.
- Concomitant medications
 - e.g. chronic steroid use
- Smoking (history of, or current)
- Indication
 - type of hearing loss
 - monaural / bilateral
 - side(s) of surgery

10.2 Surgery

The surgical procedure for all patients in the investigation is described briefly in section 5.7 and in detail in the Surgical Manual and the Addendum to Surgical Manual (MONO surgical procedure).

The following information will be gathered by the surgeon in relation to the surgery:

- Duration of surgery (see section 10.2.1)
- Implant and abutment details
- Surgical instrument information (reusable surgical instruments)
- Skin thickness, incl. measurement method
- Skin punch size
- Bone quality (see section 10.2.2)
- Implant insertion torque
- No. of turns of the insertion indicator
- If manual tightening using a counter torque wrench was needed/Performed?
 - If yes, no. of additional turns needed to seat the implant
- Type of anaesthesia used (general, local, or both)
- Medications given perioperatively
- Intra-operative events (see section 10.2.3)

10.2.1 Duration of surgery

The length of surgery [minutes] from punch to placement of healing cap. If performed, implant stability quotient (ISQ) measurements should not be included in this time registration.

CONFIDENTIAL

10.2.2 Bone quality

Quality of bone assessed subjectively by the investigator during surgery. Investigator will indicate quality with the following designators: 'Very soft', 'Soft', 'Medium', 'Hard' and 'Very hard'.

10.2.3 Intra-operative events

During the surgery intra-operative events and complications will be assessed by the surgeon.

Expected intra-operative events and complications includes, but are not limited to:

- Skin and bone bleedings
- Vein and sigmoid sinus exposure or damage
- Dura exposure or damage
- CSF leakage
- Insufficient bone volume or unexpected anatomy
- Angled insertion of the implant
- Re-positioning of the implant from initially chosen location (drilling at more than one site)
- Adding/using extra material at the implant site, like bone wax or Gore-tex.

Note: If an event is judged as untoward (exceeding what is normally expected according to surgeon's judgement) it should be reported as an adverse event.

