7.1.1 Risks associated with use of the Ponto system

Patients who meet the indications for implantation should be informed about typical risks associated with surgery (effects from general anesthesia, infections, etc.), which are independent of the product itself. This also includes temporary numbness and/or pain that could occur during the healing period.

Serious complications during surgery (e.g. heavy bleeding (not controlled using standard hospital practice), epidural hematoma, intracranial injury) are rare, but should be carefully considered. No reports of the mentioned complications have so far been identified through the company's Post Market Surveillance.

Explantation may be required e.g. in the following cases: device failure (e.g. caused by head trauma), medical or surgical complication (persistent skin infection), need of radiation therapy, or

deterioration of hearing (outside of indicated use). Often, but not always, the abutment alone can be removed, leaving the implant in position under the skin; this is in most cases a minor procedure and requires no additional surgery.

Harm associated with the implant surgery (such as persistent numbness and/or pain) and use, (such as skin overgrowth) are accounted for in the risk analysis. These risks have been evaluated, and the materials and design of the implant have been chosen to minimize these risks.

Minor infections may occur in the area of the percutaneous abutment during use and are often handled by local treatment (hygienic recommendations to avoid local infections are made in the Surgical Manual).

The use of the sound processor carries low risks (typically temporary discomfort or that the patient is unaided if e.g. the device malfunctions). Hazardous situations can however occur, e.g. if a battery is swallowed and leakage of the content occurs. These risks have been mitigated as far as possible by design of the sound processor.

In summary, the risks identified in the risk management process are typical for percutaneous implant systems. Similar systems have been on the market for several years without any reports of major complications. All identified risks have been reduced as far as possible and all residual risks are anticipated to be acceptable (according to the company's risk acceptability criteria) and outweighed by the medical benefits of the Ponto bone anchored hearing system.

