19.3 Reporting of Adverse Event(s)

All health problems*, whether judged as related to the surgery and/or the Ponto products or not, that are reported by the subject, found in medical records or found at the clinic visits must be recorded by the PI, or authorised designee, in the eCRF as an AE, preferably within 5 working days. For events judged as related, i.e. ADEs, additional information is required as specified in eCRF.

**except those defined and excluded from the investigation.*

19.3.1 *Reporting of Serious Adverse Event / (Unanticipated) Serious Adverse Device Effect*

In addition to the information already collected and recorded for AEs/ADEs, there are more detailed information required for SAEs/SADEs/USADEs as specified in eCRF.

For SAEs/SADEs/USADEs the Investigator must:

- Record SAE/SADE/USADEs details in the eCRF immediately, but no later than **24 hours** after becoming aware of the event. An email to Oticon Medical will automatically be generated by the EDC system after investigator signing of the SAE form by the Investigator. In addition, an email shall be sent to responsible clinical trial manager (to notify the SAE/SADE/USADE).
- Follow up the initial SAE/SADE/USADEs information as soon as new information is available.
- Report SAE/SADE/USADEs to the EC according to local requirements (e.g. per event and/or annually). In multicentre investigations this may include the SAE/SADE/USADEs reported from another site; this information will be provided by Oticon Medical, if required.
- Provide Oticon Medical with all SAE/SADE/USADEs related documentation and correspondence to the EC.

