19.4 Non-reportable events

When performing a BAHS surgery, some intra- and post-operative events are more or less likely to occur (i.e. not 'untoward' per se) (see sections 10.2.3 and 10.3.5). Therefore, in this investigation, the following events will be captured in the eCRF on the applicable study visit. To avoid double-reporting, these events will not be recorded in the AE log, unless the investigator judges them to exceed the level of what is to be expected (i.e. 'untoward' per se):

During surgery;

- Drilling into veins
- Drilling into air pockets
- Dura mater exposed

Post-operative complications

- Bleeding or hematoma
- Pain or numbness
- Skin dehiscence
- Erythema
- Edema
- Granulation tissue
- Skin reactions
- Revision surgery

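### Sections 10.2.3 and 19.3/19.4 give sites different answers on whether a CSF leak or dura damage is logged as an adverse event

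*Combined protocol and SAP*

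**What the plan says.** Section 10.2.3 sets out what the surgeon assesses during the operation. It opens with "Expected intra-operative events and complications includes, but are not limited to" and includes "Dura exposure or damage", "Vein and sigmoid sinus exposure or damage" and CSF leakage, along with routine items such as skin and bone bleeding, re-positioning and the use of bone wax. A note under the list reads: "If an event is judged as untoward (exceeding what is normally expected according to surgeon's judgement) it should be reported as an adverse event".

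Section 19.3 states the general rule. "All health problems*, whether judged as related to the surgery and/or the Ponto products or not" must be recorded as an AE, with one footnoted exception: "except those defined and excluded from the investigation".

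Section 19.4 supplies the exclusions. It says that some events are likely enough in this surgery not to be untoward in themselves, and cites 10.2.3 and 10.3.5 for them. It then lists the events to be kept out of the AE log unless they exceed expectation. The intra-operative part has three items: drilling into veins, drilling into air pockets, and "Dura mater exposed".

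The safety endpoint in 8.3 counts related AEs and device deficiencies at 3 and 12 months.

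**The concern.** The section that lists the surgical events and the section that exempts events from AE logging do not cover the same ground. A site working from 10.2.3 may treat a CSF leak or dural injury as an AE at the surgeon's discretion. A site working from 19.3 and 19.4 would log it by default. Because 19.4 cites 10.2.3, both readings have some support in the text.

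What is at stake is the safety result on the point where this device is new. The kit replaces three drilling steps with one (4.2). Section 7.1.2 says that the probability of harm could differ and that no clinical data exist on the final design. Injury beyond the bone is among the outcomes that bear most directly on a drill, and its AE count could depend on which section each of seven sites follows.

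**Working it through.** There is no figure in the plan to reproduce on this point. The check is a comparison of the lists, followed by tracing where the data go.

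**Step 1: the lists side by side**

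| Intra-operative event | Listed in 10.2.3 | Exempt in 19.4 | Result under 19.3/19.4 |
|---|---|---|---|
| CSF leakage | Yes | No | AE by default |
| Dura damage | Yes | No (exposure only) | AE by default |
| Dura exposure | Yes | Yes | Not an AE unless beyond expectation; agrees with 10.2.3 |
| Sigmoid sinus damage | Yes | Not named; could be read as drilling into veins | Unclear |
| Vein damage | Yes | Yes, as drilling into veins | Agrees with 10.2.3 |
| Skin and bone bleeding | Yes | No; bleeding is listed only as post-operative | AE by default on a strict reading |
| Air pockets | Not named | Yes | Not an AE unless beyond expectation |

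The mismatch is clearest for CSF leakage and dura damage. Sigmoid sinus damage is ambiguous.

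**Step 2: can the two rules be read as one?** The exclusion in 19.4 is worded for the events that it lists, so it does not clearly import the longer list in 10.2.3. Its reference to 10.2.3 nevertheless invites a site to treat that list as not untoward in itself. The AE definition in 19.1 pulls the other way, since it covers unintended injury with no condition that the surgeon find it untoward.

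**Step 3: where the event goes if it is not logged as an AE.** Intra-operative events are recorded at Visit 2 (Table 4, 9.2.2, 10.2), so the event is captured. The outputs are another matter:
- 6.2 says that the safety endpoint comprises adverse events, both intra- and post-operative.
- 8.3, 10.4 and 12.3 build the safety output from AEs, serious adverse events (SAEs) and device deficiencies.
- 8.2 has an objective for post-operative events (F) and none for intra-operative events.

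No listed endpoint or analysis uses the intra-operative event form.

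**Step 4: the SAE link.** Under 19.1.1 an SAE is an AE that led to a serious outcome, and the 24-hour duty in 19.3.1 follows from that status. Classification as an AE therefore comes first, but the event must also meet a 19.1.1 criterion before anything changes here.

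**Step 5: scale.** Assume one event among the 50 planned patients (9.4.3), with exact (Clopper-Pearson) limits.
- Logged: 1/50 = 2.0%. Lower limit 1 − 0.975^(1/50) = 0.05%. Upper limit, the 0.975 quantile of Beta(2, 49), = 10.6%.
- Not logged: 0/50 = 0%. Upper limit 1 − 0.025^(1/50) = 7.1%.

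Each reclassified patient moves the AE rate by 1/50 = 2.0 percentage points. The single event is an assumption, because the documents give no expected frequency.

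**The case against.** The best defence is that the sections divide the work: 10.2.3 says what to capture, 19.3 says to log every health problem, and 19.4 alone removes events from the log. The note in 10.2.3 says when to report and never says that other events stay out. On that reading a CSF leak is an AE and nothing conflicts. In addition, *expected* may mean only foreseeable, the event remains on the surgery form, and the safety analysis is descriptive, so no test turns on it.

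Part of this stands. The sections can be harmonised by a careful reader, and *only if untoward* is the natural sense of the note rather than its literal wording. But a note that makes reporting follow from exceeding expectation, placed under a list headed as expected and cited by 19.4, will not be read in one way at every site. Capture on a form that feeds no output does not put the event into the safety results.

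Four stronger readings are tempting, and the documents do not support them:
- *Serious events will escape expedited reporting.* That needs a surgeon to regard an event meeting a 19.1.1 criterion as no more than normal. Both 10.2.3 and 19.4 restore AE status when expectation is exceeded, and the 19.1 definition favours reporting.
- *Section 7.1.1 classes these very events as serious and rare.* It says "Serious complications during surgery (e.g. heavy bleeding (not controlled using standard hospital practice), epidural hematoma, intracranial injury) are rare", which does not name CSF leakage, dura damage or sinus damage. The tension with an *expected* label is one of tone.
- *Sigmoid sinus damage is plainly outside 19.4.* It may fall under drilling into veins.
- *The remedy is to confine the 10.2.3 note to the three events in 19.4.* That would make routine skin or bone bleeding an AE by default, against the aim in 19.4 of avoiding double reporting.

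**Conclusion.** The point holds as an inconsistency in the AE rule. For CSF leakage and dura damage, and less clearly for sigmoid sinus damage, the plan supports two answers on whether the event is logged by default or on the surgeon's judgement. Sites may therefore differ on what enters the safety endpoint, and nothing in the listed analyses recovers an event left on the surgery form.

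The size cannot be estimated from the documents. One event would be the difference between 1/50 and 0/50 in the AE table; how often that would arise is unknown, and many surgeons might report such an event anyway. The conclusion rests on the wording of 10.2.3, 19.3 and 19.4 and on the absence of any listed output for intra-operative events. A reader might infer that the events are lost or that SAE reporting fails. The documents show neither: the events are recorded, and the SAE consequence is conditional.

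**What to change.** Reconcile 10.2.3 with 19.3 and 19.4 into one list and one AE rule, used in both places:
- Keep the unless-untoward exemption for routine items, for example skin and bone bleeding, re-positioning, bone wax, exposed dura and air pockets.
- State that CSF leakage, dura damage and any event meeting a 19.1.1 criterion are entered as AEs, with SAE assessment.
- Say whether sigmoid sinus damage counts as drilling into veins.
- Add to 12.3 a table of the intra-operative event form, shown beside the AE tables.

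The cost is a few sentences of text and a short notice to sites, with possibly a few more AE forms and one more table. The change concerns safety reporting only and leaves patient care untouched.
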